6.5.3 Baseline characteristics

The following relevant patient baseline characteristics will be listed and summarized overall (frequency and percentage) and are considered key subgroups, and will only be used for presentations of the primary endpoint in Extension phase I analyses:

- Naïve versus non-naïve, as determined at screening during the Parent study phase
- Age (paediatric versus adult) at Visit 7
- Gender (male versus female)

Clinical Study Reference: IB1001-202

- Age/weight/dosing group as applicable at Visit 7
- Selected Primary Anchor Test (9HPT-D or 8MWT) as defined during the Parent study phase
- Tay-Sachs versus Sandhoff Patients
- Composite of SARA Subtests 1- 4 (Gait, Stance, Sitting, Speech): classification based on below(≤)/above the median value at Visit 7
- Age of diagnosis: Infantile (<2 years), Juvenile (2 to <15 years), Adolescent/Late Onset (≥ 15 years)
- Disease severity: classification based on below (≤)/ above the median SARA total score at Visit 1.

6.5.4 Disposition

A summary table will be created, stating the number of patients per site, including site number, location/country, and investigator.

To present disposition, a summary of all included, treated, and completed patients will be created for the Extension phase I and II separately, and for the full Extension phase . Additionally, in the same summary, the number/percentage of patients in the SAFe and mITTe will be presented. Furthermore, the frequency and percentage per reason for non-completion will be added.

A listing displaying all disposition information (including reasons for withdrawal and reasons for exclusion from the analysis population, if available electronically) on a per patient level will be created. This listing will include follow-up time for each patient, calculated from date of first dose during the Extension phase until end of Extension phase or withdrawal date.

6.5.5 Medical history

Note that only for patients not having a seamless transition from the Parent study to the Extension phase, additional medical history data may be collected during the intermediate time. Medical history will be tabulated per System Organ Class (SOC) and Preferred term (PT) according to the Medical Dictionary for Regulatory Activities (MedDRA) terminology list and presented as number/percentage of patients in each SOC and PT for the SAFe. SOC and PT will be presented in descending order of frequency of occurrence based on SOC and PT. These data will also be listed on a per patient level.

6.5.6 Pregnancy data

Pregnancy test result data will be listed for females of childbearing potential only, on a per visit basis.

6.5.7 Other screening data

Other data collected at screening and/or baseline only, if available, will be listed. These screening/baseline data will be presented using all subjects included in the Extension phase, if applicable.

6.6 Statistical analysis efficacy endpoints

The analysis for all efficacy endpoints in the Extension phase is the mITTe.

Analyses of the primary endpoint based on the mITTe population will utilise a last observation carried forward (LOCF) approach for missing mDRS at Visit 9. For the primary mDRS endpoint this implies that the measurement of Visit 8 will be used instead. Other endpoints will not be imputed, and missing data will be reported as is. No sensitivity analyses will be applied.

For the primary endpoint for the Extension phase there will be separate descriptive statistical displays within the key subgroups as listed in Section 6.5.3, without any statistical analysis. For the subgroup presentations, only the mITTe population will be used. No plots will be created. All individual primary endpoint data will be listed as well.

All efficacy endpoints for Extension phase Visit 10 to Visit 12 are considered exploratory, and therefore described under section 6.6.4.

6.6.1 Primary endpoint Extension phase

The primary efficacy endpoint is based on the Modified Disability Rating Scale (mDRS). The mDRS measures neurological status via clinical signs and symptoms in 6 domains (ambulation, language, manipulation, swallowing, seizures, and ocular movement). A higher mDRS score indicates a clinical worsening, while a lower mDRS score indicates a clinical improvement. A 0-point change in the mDRS score represents a stabilization of disease progression, which is also considered a significant clinical improvement.

The mDRS composite score and individual domains, including change values, will be summarized using descriptive statistics at each visit for Extension phase.

The primary endpoint in this Extension Phase is success measured on the mDRS score from the Extension Phase baseline (Visit 7) to the end of treatment in the Extension Phase (Visit 9). Success is defined as no change or a decrease in mDRS score from Visit 7 to Visit 9.

The primary endpoint will be summarized using a frequency table. The primary statistical analysis of comparing the proportion success with the null proportion of 0.10 will be done using a one-sided Fisher's Exact Test, expecting an increase in the success rate. The statistical result (one-sided p-value and exact 90% confidence interval²) will be added to the frequency table. This analysis is considered to be exploratory.

In addition, a spaghetti plot presenting the total mDRS scores of each patient through time will be created.

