8.5.1 Primary Efficacy Endpoint

The primary endpoint is based on the modified Disability Rating Scale (mDRS) score with success defined as no change or a decrease in the mDRS score from Visit 7 to Visit 9.

It is postulated that under standard of care, 90% of patients would worsen (higher score) in terms of their performance on the mDRS scale over a 12-month period, while conversely only 10% would show similar performance or some improvement. Statistical evaluation of the primary binary endpoint (success/failure on mDRS scale) will compare the proportion of success with 10% in a one-sided Fishers Exact test at the one-sided 5% significance level.

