2.4.2 Extension phase

The sample size is determined by the number of patients that move into this Extension phase from the Parent study. The expectation is that between 60% and 70% of patients will rollover into the extension period. With 20 out of 32 patients (62.5%) rolling over, the study will have 80% power to detect an improvement in the success rate to 31% compared to the null hypothesis value of 10%.

Patients who completed Visit 10 of the Extension phase and are willing to continue for an additional year will continue in the Extension Phase until Visit 12.

Clinical Study Reference: IB1001-202

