4.2.1 Primary endpoint

The primary endpoint in the Extension phase is "success" based on the mDRS score, with success defined as no change or improvement (decrease) in the mDRS score from Visit 7 to Visit 9.

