6.2 Adjudication of endpoint data

Videos of the primary and non-primary anchor tests are collected throughout the extension phase for the CI-CS. These videos may be analyzed in order to inform the development and validation of the CI-CS but will not be reported in the CSR (and hence not listed or tabulated). Data received will be included as-is in the CDISC files. In case of analysis, the following process applies: For the CI-CS assessments of both the primary and non-primary anchor tests, after a patient completes Visit 10 of the Extension phase, the independent raters will be given 3 video pairs of from Visit 7 to Visit 9, Visit 9 to Visit 10, and Visit 7 to Visit 10. After a patient completes Visit 12 of the Extension phase, the independent raters will be given a video pair from Visit 10 to Visit 12 (the raters may also assess additional video pairs, i.e. Visit 1 to Visit 12, on an exploratory basis). After a patient completes Visit 12 of the Extension phase, the independent

Clinical Study Reference: IB1001-202

raters will be given a video pair from Visit 10 to Visit 12 (the raters may also assess additional video pairs, i.e. Visit 1 to Visit 12, on an exploratory basis). The videos will be presented in a random order, and the independent raters will be blinded to the timepoint corresponding to each video. The appropriate Likert scale score will be provided to each of the videos and pairs of videos. For further details regarding scoring and adjudication, which will be similar to that of the Parent study, see Section 5.2.

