6.6.3 Exploratory Endpoints

All exploratory endpoints for the Extension phase will be presented using the mITTe population, and all individual data will be listed as well. For all exploratory endpoints, the change from Visit

² The exact CI and the p-value using the Fisher's Exact test can contradict each other, especially in small sample sizes. Therefore, the exact CI will include a mid-p adjustment.

Clinical Study Reference: IB1001-202

7 to Visit 9 will be evaluated. No statistical analysis other than descriptive statistics will be done. No plots will be created.

Measurement of Ataxia and Functioning

- SARA total score
- SCAFI total score
 - o 9HPT-D
 - o 9HPT-ND
 - o 8MWT
 - o PATA test

Descriptive statistics will be used to summarize the endpoints above at each visit.

The subscores of the SARA score (gait, stance, sitting, speech disturbance, finger chase, nose-finger test, fast alternating hand movements, heel-shin slide) will not be summarized separately, and only listed.

The average SCAFI subscores (8MW_avg, 9HPT-D_avg, 9HPT-ND_avg and PATA_avg) as determined according to Section 10.1, following the scoring manual, will also be summarized with descriptive statistics.

The changes in SARA total score, SCAFI total score, and the SCAFI subscores (8MW_avg, 9HPT-D_avg, 9HPT-ND_avg and PATA_avg) between Visit 7 and Visit 9, and Visit 10 and Visit 12, will be descriptively summarized in tabular format as well.

Measurement of Health-related Quality of Life

The results of EQ-5D-5L as well as the EQ-5D-Y will be combined into a 5-digit number presenting the health status of the subject. Frequency tables will be presented per visit for the 5 domains, as well as for the 5-digit number of the EQ-5D-5L and the EQ-5D-Y separately.

Note that if a patient turns 18 before Visit 7, this patient can have results on EQ-5D-Y in the Parent Study, and results on EQ-5D-5L in the Extension phase Visit 7 to 10. For this reason, separate QoL presentations will be created for Extension phase I, using Visit 7 measurements as baselines. The EQ-VAS score will be summarized by visit using descriptive statistics in a combined manner for patients aged < and ≥ 18 years (using Visit 7 age values).

Measurement of Global Impression

The three CGI-S scores (scored by treating physician, caregiver, and patient) will be summarized using descriptive statistics and frequency tables for each visit.

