14.2 Efficacy Data Summary figures and Tables	
14.2.63	Frequency table, p-value, and CI on the primary endpoint CI-CS success rate (mITTe)
14.2.64	Descriptive statistics on CI-CS scores on the primary anchor, including change values between visits (mITTe).
14.2.65	Frequency table of the primary endpoint CI-CS success rate according to subgroups (mITTe).
14.2.66	Descriptive statistics of the primary endpoint CI-CS, including change values between visits, according to subgroups (mITTe).
14.2.67	Frequency table of the success rate of CI-CS score for the non-primary anchor test (mITTe)

14.2.68	Descriptive statistics of the CI-CS score for the non-primary anchor test, including change values between visits (mITTe)
14.2.69	Frequency table of the success rate of CI-CS score for the non-primary anchor test according to subgroups (mITTe)
14.2.70	Descriptive statistics of the CI-CS score for the non-primary anchor test, including change values between visits, according to subgroups (mITTe)
14.2.71	Descriptive statistics of the SARA total score and 8 subscores at each visit, including change values between visits (mITTe)
14.2.72	Descriptive statistics of the SARA total score and 8 subscores at each visit, including change values between visits, according to subgroups (mITTe)
14.2.73	Descriptive statistics of the SCAFI total score and subscores 8MW_avg, 9HPT-D_avg, 9HPT-ND_avg and PATA_avg at each visit, including change values between visits (mITTe)
14.2.74	Descriptive statistics of the SCAFI total score and subscores 8MW_avg, 9HPT-D_avg, 9HPT-ND_avg and PATA_avg at each visit, including change values between visits, according to subgroups (mITTe)
14.2.75	Frequency table of the EQ-5D-5L and EQ-5D-Y health status and 5 subdomains at each visit (mITTe)
14.2.76	Frequency table of the EQ-5D-5L and EQ-5D-Y health status and 5 subdomains at each visit according to subgroups (mITTe)
14.2.77	Descriptive statistics of the EQ-VAS for -5L and -Y combined at each visit (mITTe)
14.2.78	Descriptive statistics of the mDRS total score and 8 subscores at each visit, including change values between visits (mITTe)
14.2.79	Descriptive statistics of the mDRS total score and 8 subscores at each visit, including change values between visits, according to subgroups (mITTe)
14.2.80	Frequency table of the 3 CGI-S scores (treating physician, caregiver, and patient) at each visit (mITTe)

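### The Extension primary analysis names a two-group test for one group against a fixed 10%, pairs it with an interval that can contradict the p-value, and lists its output under the wrong endpoint

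*SAP*

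**What the plan says.** All Extension patients receive the study drug and there is no comparator. SAP 4.2.1 sets the endpoint as "success defined as no change or improvement (decrease) in the mDRS score from Visit 7 to Visit 9". For its analysis, SAP 6.6.1 states that "comparing the proportion success with the null proportion of 0.10 will be done using a one-sided Fisher's Exact Test". Protocol Appendix 6, section 8.5.1, agrees: the evaluation "will compare the proportion of success with 10% in a one-sided Fishers Exact test at the one-sided 5% significance level".

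The SAP reports a one-sided p-value with an exact 90% confidence interval. Footnote 2 to SAP 6.6.1 warns that the interval and a Fisher p-value may disagree in small samples, and concludes: "Therefore, the exact CI will include a mid-p adjustment". No such adjustment is stated for the p-value.

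On size, SAP 2.4.2 expects 60% to 70% of patients to roll over and says: "With 20 out of 32 patients (62.5%) rolling over, the study will have 80% power" to detect a success rate of 31% against 10%.

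The output list in SAP 12.3 describes Table 14.2.63 as "Frequency table, p-value, and CI on the primary endpoint CI-CS success rate (mITTe"). SAP 6.2 says of the Extension CI-CS data that they may be analysed to develop the scale "but will not be reported in the CSR (and hence not listed or tabulated").

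SAP 6.6.1 adds: "This analysis is considered to be exploratory".

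**The concern.** There are three faults in one analysis.

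- **The test.** Fisher's exact test works on a 2×2 table of two observed groups. A single observed proportion and the constant 0.10 do not supply the second row, so a programmer must either invent a comparator or silently substitute another test.
- **The interval.** Applying mid-p to the interval but not to the p-value makes them answer to different rules. The report could then show a non-significant p-value beside an interval that excludes 10%, which is the outcome the footnote sets out to prevent.
- **The output list.** The only table carrying the p-value and interval is labelled CI-CS success, not mDRS success. No listed table gives the mDRS success rate, its test or its subgroup breakdown.

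At stake is whether the Extension's only formal test can be reproduced and is reported under its own endpoint. The Parent Study conclusion is not affected.

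**Working it through.** **Inputs.** Null rate 0.10, alternative 0.31, n = 20 and stated power 80% (SAP 2.4.2); one-sided 5% level (Protocol Appendix 6, 8.5.1); two-sided 90% interval (SAP 6.6.1); roll-over of 60% to 70% of 32. Since 0.60 × 32 = 19.2 and 0.70 × 32 = 22.4, the whole numbers in that range are 20, 21 and 22.

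**Step 1: reproduce the plan's power.** For the one-sample exact binomial test, p = P(X ≥ x | n, 0.10).

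- At n = 20, P(X ≥ 4 | 0.10) = 0.133 and P(X ≥ 5 | 0.10) = 0.0432, so the test rejects at 5 or more successes.
- Power is P(X ≥ 5 | 20, 0.31) = 0.791, in line with the stated 80%.

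A Fisher test needs an assumed second group, and with one it does not reproduce the figure. Against a fixed 2/20 the power is 0.259, against a fixed 20/200 it is 0.621, and against a random comparator of 20 patients at 10% it is 0.369. These comparators are assumptions made only to show the range. So the sample size stands and the name of the test is wrong.

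**Step 2: what the missing second row does.** For the same 5/20 successes, p is 0.043 by the exact binomial, 0.059 by Fisher against 20/200, and 0.204 by Fisher against 2/20. The answer depends on a choice that the plan does not make.

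**Step 3: interval against p-value.** For x successes, the lower 90% limits solve:

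- Clopper-Pearson: P(X ≥ x | p) = 0.05. This limit exceeds 0.10 exactly when the one-sided exact p-value is below 0.05, so the two cannot disagree.
- Mid-p: P(X > x | p) + ½ P(X = x | p) = 0.05. This limit exceeds 0.10 when the mid-p value, which is always smaller than the exact p-value, is below 0.05. Conflict arises whenever the mid-p value is below 0.05 and the exact p-value is above it.

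At 5/21, P(X ≥ 5 | 0.10) = 0.0522 and P(X ≥ 6 | 0.10) = 0.0144, so the mid-p value is (0.0522 + 0.0144)/2 = 0.0333. At 5/22 it is (0.0621 + 0.0182)/2 = 0.040.

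| Result | Exact p | Clopper-Pearson lower | Mid-p lower | Mid-p agrees with p? |
|---|---|---|---|---|
| 4/20 | 0.133 | 0.071 | 0.083 | yes |
| 5/20 | 0.043 | 0.104 | 0.117 | yes |
| 5/21 | 0.052 | 0.099 | 0.111 | no |
| 5/22 | 0.062 | 0.094 | 0.106 | no |

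At the planned 31% rate, exactly 5 successes has probability 0.154 at n = 21 and 0.137 at n = 22.

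Over n = 18 to 39, Clopper-Pearson never conflicts. Mid-p conflicts at one count for each of n = 21, 22, 23, 28 to 30 and 35 to 37. If roll-over were taken from the 39 planned for enrolment (0.60 × 39 = 23.4 and 0.70 × 39 = 27.3, so n = 24 to 27), no conflict would occur.

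**Step 4: the output list beside the analysis text.**

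- SAP 4.2.1 and 6.6.1 and Protocol Appendix 6 section 8.5.1 define the endpoint as mDRS success. Tables 14.2.63 and 14.2.65 show the primary endpoint as CI-CS success, overall and by subgroup.
- SAP 6.2 excludes Extension CI-CS from tables and listings. Tables 14.2.63 to 14.2.70 and listing 16.2.5.9 present it.
- The mDRS tables, 14.2.78 and 14.2.79, are descriptive only. They refer to eight subscores, while SAP 6.6.1 names six domains.

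**The case against.** The fair case against is about weight and remedy.

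SAP 6.6.1 gives one proportion, a null value, a direction and an exact interval, so most statisticians would read the test as the exact binomial. The analysis is exploratory, SAP section 7 ties trial success to the Parent Study endpoint, and SAP 6.1 gives point estimates equal emphasis with significance. The interval conflict needs an unadjusted binomial p-value, is absent at the planned n = 20, and affects one count at n = 21 and one at n = 22. The CI-CS tables look like leftovers: the SAP defines no CI-CS success rule or null rate for the Extension, so Table 14.2.63 could not be produced from the plan as written. Mid-p for both the p-value and the interval would also remove the conflict. Changing the protocol may require a formal amendment under Protocol 11.3.

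Much of this stands, and it limits the weight of the point. It does not remove it. Both documents name Fisher's test and footnote 2 reasons from a Fisher p-value, so the intended test has to be guessed. SAP 6.1 calls a one-sided p below 0.05 statistically significant for the primary endpoint. SAP 12.3 says that its tables will be prepared as numbered. The matched mid-p option has a cost: rejecting at 5 or more successes has a true size of 0.052 at n = 21 and 0.062 at n = 22, above the stated 5%.

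**Conclusion.** The concern holds on all three parts. The named test does not fit one group against a constant, and the plan's own power identifies the one-sample exact binomial as the intended test. Mid-p on the interval alone creates a contradiction that Clopper-Pearson would not have. At the planned success rate its probability is about 15% if 21 patients roll over, 14% if 22 do, and zero if 20 do. This assumes that the p-value is the exact binomial one and that roll-over is counted from 32 patients. The output list contradicts both the endpoint definition and SAP 6.2; that part rests on no assumption.

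The size is modest: the result is exploratory, and the Parent Study conclusion does not depend on it.

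The exact power at 31% drops to 67% at n = 21 and 72% at n = 22, where 6 successes are needed. That is the ordinary step pattern of an exact test and not a further fault.

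**What to change.** - In SAP 6.6.1 and Protocol Appendix 6 section 8.5.1, specify a one-sided one-sample exact binomial test of 0.10 at the 5% level, with the two-sided 90% Clopper-Pearson interval. SAP section 7 can record the change until the protocol is next amended.
- Delete footnote 2.
- Change Tables 14.2.63 and 14.2.65 to mDRS success.
- Remove Tables 14.2.64 and 14.2.66 to 14.2.70 and listing 16.2.5.9, or replace them with mDRS where Tables 14.2.78 and 14.2.79 and listing 16.2.5.13 do not already cover it.
- In Tables 14.2.78 and 14.2.79, correct the number of subscores to the six mDRS domains.

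The cost is wording and edits to the output list. Data, sample size and stated power stay as they are. The interval becomes slightly wider: at 5/20 it is 0.104 to 0.456 in place of 0.117 to 0.434.

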6.6.2 Key secondary endpoints Extension phase

As PK is handled by an external company, there are no analyses for secondary endpoints to add here.

6.6.3 Exploratory Endpoints

All exploratory endpoints for the Extension phase will be presented using the mITTe population, and all individual data will be listed as well. For all exploratory endpoints, the change from Visit

² The exact CI and the p-value using the Fisher's Exact test can contradict each other, especially in small sample sizes. Therefore, the exact CI will include a mid-p adjustment.

Clinical Study Reference: IB1001-202

7 to Visit 9 will be evaluated. No statistical analysis other than descriptive statistics will be done. No plots will be created.

Measurement of Ataxia and Functioning

- SARA total score
- SCAFI total score
 - o 9HPT-D
 - o 9HPT-ND
 - o 8MWT
 - o PATA test

Descriptive statistics will be used to summarize the endpoints above at each visit.

The subscores of the SARA score (gait, stance, sitting, speech disturbance, finger chase, nose-finger test, fast alternating hand movements, heel-shin slide) will not be summarized separately, and only listed.

The average SCAFI subscores (8MW_avg, 9HPT-D_avg, 9HPT-ND_avg and PATA_avg) as determined according to Section 10.1, following the scoring manual, will also be summarized with descriptive statistics.

The changes in SARA total score, SCAFI total score, and the SCAFI subscores (8MW_avg, 9HPT-D_avg, 9HPT-ND_avg and PATA_avg) between Visit 7 and Visit 9, and Visit 10 and Visit 12, will be descriptively summarized in tabular format as well.

Measurement of Health-related Quality of Life

The results of EQ-5D-5L as well as the EQ-5D-Y will be combined into a 5-digit number presenting the health status of the subject. Frequency tables will be presented per visit for the 5 domains, as well as for the 5-digit number of the EQ-5D-5L and the EQ-5D-Y separately.

Note that if a patient turns 18 before Visit 7, this patient can have results on EQ-5D-Y in the Parent Study, and results on EQ-5D-5L in the Extension phase Visit 7 to 10. For this reason, separate QoL presentations will be created for Extension phase I, using Visit 7 measurements as baselines. The EQ-VAS score will be summarized by visit using descriptive statistics in a combined manner for patients aged < and ≥ 18 years (using Visit 7 age values).

Measurement of Global Impression

The three CGI-S scores (scored by treating physician, caregiver, and patient) will be summarized using descriptive statistics and frequency tables for each visit.

Descriptive statistics and frequency tables will also be used to summarize the three CGI-C scores (treating physician, caregiver, and patient) between Visit 7 and Visit 9.

Note that CGI-C is mentioned as CGI-I in the eCRF.

It is important to realize that the CGI-S and CGI-C scores per visit for each patient as provided by the caregiver may be based on varying caregivers and hence additional variation is introduced. No correction for this variation can be done and a footnote will be added to the table to describe this situation.

Clinical Study Reference: IB1001-202

